Contributing authors	PPD is taking the role of study statistician and replaces PPD	Personnel change

Section # and Name	Description of Change	Brief Rationale
Section 2: objective	
Add ‘to evaluate the proportion of patients achieving health status response with Trelegy.’ as the third secondary objective
 
Add an additional secondary outcome to see CAT score change at week 4
	
Align with study endpoints
 
Align with study objectives

Section 3.2.1. Withdrawal from Trelegy or the Study	Add ‘Any female participant who becomes pregnant while participating will be withdrawn from the study.’	For clarification
Section 3.3 study population	
Update study site to 30
 
Replace ‘Based on local market research data, the proportion of participants taking free combination of triple therapy and with LAMA/LABA at baseline will be no more than 25% of all enrolled participants to reflect the real-world status of COPD maintenance treatment pattern in China.’ with ‘Based on local market research data, the proportion of participants with different baseline maintenance treatments in this study may be adjusted during enrolment stage to reflect the real-world status of COPD maintenance treatment pattern in China.’
	Update. Remove threshold for baseline pre-existing treatment to add flexibility in recruitment.
Section 3.4.1 inclusion criteria	replace ‘who have been prescribed it continually for at least 12 weeks’ with ‘with no minimum treatment duration’	To accommodate to real world clinical practice and add flexibility in recruitment
Section 3.4.2: Exclusion criteria	
Modify exclusion criteria 2 to ‘Treated with Trelegy within 3 months prior to screening (Visit 1).’
 
Replace ‘prescribed’ to ‘treated’
 
Reduce the timeframe to 3 months
	
To ensure the alignment with inclusion criteria 6 and avoid confusion.
 
To reduce the timeframe to 3 months to add flexibility in recruitment.

Section # and Name	Description of Change	Brief Rationale
Section 3.4.2: Exclusion criteria	Remove original exclusion criteria 10	Not applicable based on current China COVID-19 management policy.
Section 3.6.1.3: Pulmonary function test (spirometry) for Pre-dose FEV ₁ , FVC, FEF ₂₅₋₇₅ , IC	Remove 'Participants who are unable to perform spirometry could still have an inhaler error assessment and are not excluded from the study.'	Not applicable in the study.
Section 3.6.2.4: Electrocardiogram	Remove 'and a repeated recording used for analysis'	Correction. No recording will be used for analysis in this study.
Section 3.7.2: Sample size consideration	Change Table 2 to Table 3	Correction.
Section 5.2: Reporting of pregnancy exposures	Remove 'and/ or GSK medical affairs'	Correction. No GSK medical affairs will be involved in this procedure.
Section 3.8.2.1 Primary endpoint/ estimand	Primary analysis will be conducted using an inverse-probability weighted mixed model for repeated measures (MMRM) for the change from baseline in CAT score under the missing at random assumption to handle missingness which may occur during the data collection.	The MMRM may provide additional insights to the primary endpoint.
Section 3.8.3: Additional analysis for license renewal	Add section of additional analysis for license renewal	To add flexibility to provide data for license renewal.
Section 6	Add 'whole study'	For clarification. Whole study data will be reported. (rather than after the additional analysis for license renewal)
Throughout	Minor editorial and document formatting revisions	Minor therefore have not been summarized.

TABLE OF CONTENTS

1.	BACKGROUND AND RATIONALE	9
2.	OBJECTIVES.....	11
3.	RESEARCH METHODOLOGY	12
3.1.	Study Design	12
3.2.	Data Source / Data Collection.....	12
3.2.1.	Withdrawal from Trelegy or the Study	19
3.2.2.	Lost to Follow Up	19
3.3.	Study Population.....	19
3.4.	Eligibility Criteria	19
3.4.1.	Inclusion Criteria	19
3.4.2.	Exclusion Criteria.....	20
3.5.	Treatment	21
3.5.1.	Treatment Administered.....	21
3.5.2.	Concomitant Therapy.....	22
3.6.	Study Assessments and Procedures	22
3.6.1.	Effectiveness Assessments	22
3.6.2	Safety Assessments	23
3.7	Sample Size Calculations	25
3.7.1	Statistical assumptions	25
3.7.2	Sample size consideration	25
3.7.3	Sensitivity assessments.....	25
3.8	Data Analysis Considerations	28
3.8.1	Population for Analysis	28
3.8.2	Statistical Analysis	28
3.8.3	Additional Analysis for License Renewal.....	30
4	LIMITATIONS.....	30
5	STUDY CONDUCT, MANAGEMENT & ETHICS.....	30
5.1	AEs, Study treatment related AEs and SAEs	31
5.2	Reporting of pregnancy exposures	31
5.3	Medical Device	31
6	PLANS FOR DISSEMINATING AND COMMUNICATING STUDY RESULTS	32
7	REFERENCES.....	33
8	APPENDIX 1: QUESTIONNAIRES AND MEASURE.....	35
8.1	Appendix 1-1 CAT Assessment	35
8.2	Appendix 1-2 The mMRC.....	36
9	APPENDIX 2: STUDY GOVERNANCE CONSIDERATIONS	37
10	APPENDIX 3: AES AND SAEs: DEFINITIONS AND PROCEDURES FOR RECORDING, EVALUATING, FOLLOW-UP, AND REPORTING.....	41
10.1	Definition of AE	41
10.2	Definition of SAE.....	43
10.3	Definition of Study treatment related AEs.....	44

10.4	Recording and Follow-Up of AE and SAE	44
10.5	Reporting of SAE to GSK.....	46
11	APPENDIX 4: COLLECTION OF PREGNANCY INFORMATION.....	47

ABBREVIATIONS AND TRADEMARK INFORMATION

AE	Adverse Event
CAT	COPD Assessment Test
CDE	Center for Drug Evaluation in China
CFR	Code of Federal Regulations
CI	confidence interval
CIOMS	Council for International Organizations of Medical Sciences
COPD	chronic obstructive pulmonary disease
CRA	clinical research assistant
CSR	clinical study report
DPI	Dry Powder Inhaler
ECG	Electrocardiogram
eCRF	Electronic Case Report Form
E.D.	early discontinuation / withdrawal
EHR	Electronic Health Records
FAS	Full Analysis Set
FEF ₂₅₋₇₅	Forced Expiratory Flow at the 25 and 75%
FEV ₁	Forced expiratory volume in 1 second
FF	fluticasone furoate
FVC	Forced Vital Capacity
GCP	Good clinical practice
HIPAA	Health Insurance Portability and Accountability Act
HRQoL	health related quality of life
IC	Inspiratory Capacity
ICF	informed consent form

ICMJE	International Committee of Medical Journal Editors
ICS	Inhaled Corticosteroids
IEC	Independent Ethics Committee
LABA	Long-Acting Beta-2-Agonists
LAMA	Long-Acting Muscarinic Antagonist
MCID	minimum clinical meaningful difference
MedDRA	Medicinal Dictionary for Regulatory Activities
mMRC	Modified Medical Research Council
NDA	New Drug Application
PK	Pharmacokinetic
PFT	Pulmonary function test
RCT	Randomized controlled trial
SAE	Serious Adverse Event
SD	standard deviation
SMPC	Summary of Product Characteristics
SoA	Schedule of Activities
SRM	Study Reference Manual
WOCBP	Woman of Childbearing Potential
UMEC	umeclidinium
VI	vilanterol

Trademark Information

[figure not shown]
Trademarks of the GlaxoSmithKline group of companies	Trademarks not owned by the GlaxoSmithKline group of companies
Ellipta	
Trelegy	NONE

1. BACKGROUND AND RATIONALE

Trelegy [fluticasone furoate (FF)/ umeclidinium (UMEC)/ vilanterol (VI) (100 µg/62.5 µg/25 µg)] in a single inhaler (TRELEGY ELLIPTA) provides a recently approved treatment option for the management of patients with advanced Chronic obstructive pulmonary disease (COPD) the aim of reducing exacerbation frequency and burden of polypharmacy, improving lung function, health related quality of life (HRQoL) and symptom control, while providing a more convenient treatment option for patients compared with established dual/monotherapies.

Trelegy 100/62.5/25 µg was approved in China on 04 November 2019 for a maintenance treatment in adult patients with COPD. Data from two phase III studies and one Pharmacokinetic (PK) study supported the New Drug Application (NDA) approval in China. In the two phase III studies [[Lipson, 2018](#); [Lipson, 2017](#)], Trelegy showed significantly better improvement in the primary and secondary endpoints, including Forced expiratory volume in 1 second (FEV₁), exacerbation reduction and symptoms compared with Inhaled Corticosteroids (ICS)/ Long-Acting Beta-2-Agonists (LABA) or Long-Acting Muscarinic Antagonist (LAMA)/LABA in the overall population.

CCI

COPD refers to a progressive deterioration of lung function and a series of mental and physical comorbidities. It is one of the leading causes of morbidity and mortality worldwide, inducing substantial economic, social, and health-care burden [[GOLD, 2021](#)]. COPD is the fifth leading cause of death in China with a reported prevalence of 13.7% in people aged 40 years or older [[GBD, 2017](#)]. It is essential to provide appropriate treatments for COPD patients according to guidelines.

GOLD guideline recommends one of the goals of treatment of stable COPD is the reduction of symptoms which includes three components, i.e., to reduce symptoms, improve exercise tolerance and improve health status [[GOLD, 2021](#)]. Triple therapy (ICS/LABA/LAMA) is recommended as step-up therapy in patients with COPD whose symptoms or exacerbations are not controlled by ICS/LABA or LAMA/LABA, or with high level of blood eosinophils or comorbid with asthma [[GOLD, 2021](#)].

As high symptom burden is one of the key unmet medical needs for COPD patients even among those under the treatment of maintenance therapies, the main goal of this single-armed study is to collect the real-life effectiveness data focusing on symptoms of COPD in patients treated with Trelegy for 12 weeks, by comparison to baseline data which can reflect the benefits of patients who remain symptomatic with their prior maintenance treatment and switch to Trelegy under the discretion of their physicians. Based on previous results [[Marth, 2021](#); [Bansal, 2021](#)], a decrease over 2 unit [minimum clinical meaningful difference (MCID)] of COPD Assessment Test (CAT) score and MCID change (over 100 ml) of forced expiratory volume in one second (FEV1) were observed

for triple therapy after 12-week treatment. Therefore, a 12-week duration is considered to be enough to observe a clinical meaningful change from baseline of the study outcomes, i.e., CAT and FEV₁.

The CAT score is defined as primary outcome because it is recommended by guideline [GOLD, 2021] as the tool for assessment of disease severity and usually leveraged by physicians in daily practice to evaluate the patient's response to treatment. A decrease of 2 unit compared to baseline is considered as the MCID [Kon, 2014]. Other outcomes including lung function and dyspnea can provide data from different dimensions on effectiveness which are also clinically relevant to the evaluation of the response of patients to treatment.

2. OBJECTIVES

Primary Objective	Primary Outcome
The primary objective of this study is to evaluate the effectiveness of Trelegy on health status in patients with symptomatic COPD at week 12.	
 Change from baseline of CAT score at week 12
Secondary Objectives	Secondary Outcomes
to evaluate the effectiveness of Trelegy on dyspnea in patients with symptomatic COPD at week 12. to evaluate the effectiveness of Trelegy on lung function in patients with symptomatic COPD at week 12. to evaluate the proportion of patients achieving health status response with Trelegy. to evaluate the effectiveness of Trelegy on health status in patients with symptomatic COPD at week 4.	
 Change from baseline of Modified Medical Research Council (mMRC) at week 12 Change from baseline of pre-dose FEV₁ at week 12 Proportion of CAT responder (defined as ≥ 2 unit decrease from baseline) at week 12 Change from baseline of CAT score at week 4
Exploratory Objectives	Exploratory Outcomes
to evaluate the effectiveness of Trelegy on lung function in patients with symptomatic COPD	
 Change from baseline of Forced Vital Capacity (FVC), Forced Expiratory Flow at the 25 and 75% (FEF₂₅₋₇₅), Inspiratory Capacity (IC) at week 12
Safety Objective	Safety Outcomes
The safety objective is to collect the safety information of participants using Trelegy.	
 Trelegy related AEs SAEs AEs that lead to the discontinuation of Trelegy

3. RESEARCH METHODOLOGY

[figure not shown]
3.1. Study Design

This is a 12-week, prospective, open label, single cohort study. The enrolled participants will be those who are symptomatic under COPD maintenance treatments, and newly prescribed with Trelegy under the discretion by clinical physicians.

The study applies a single cohort design to evaluate the effectiveness following 12-week treatment with Trelegy by comparison to baseline data, which can reflect the benefits (i.e., CAT score and FEV₁, etc.) of patients who remain symptomatic with their prior maintenance treatment. The decision to prescribe Trelegy shall be independent to the study with medical records providing documentation of a Trelegy prescription.

The prospective data collection starts from Visit 1 when Trelegy is taken by patients for the first dose (see [Figure 1](#) below). The participants will complete the CAT score at Visit 1, Visit 2 and Visit 3 or early discontinuation/withdrawal visit (E.D.), and the mMRC at Visit 1 and Visit 3 or E.D. The participants' pulmonary function test will be assessed at Visit 1 and Visit 3 or E.D.. The investigators will record Trelegy-related adverse events (AEs), serious adverse events (SAEs) and AEs that lead to withdrawal from Trelegy.

Figure 1 The Schematic diagram for this study

* : V0 and V1 could occur on the same day, and V1 should be completed ≤7 days after V0.

3.2. Data Source / Data Collection

The investigators will enroll participants by assessing the inclusion/exclusion criteria. The patients will be enrolled at visit 1 and will be followed up prospectively for 12 weeks.

During this trial the following information and measurements will be collected, and the details are listed in [Table 1](#):

To be completed at Visit 1:

- Patient demographics (including sex, age, height, weight)
- Patient past medical history and co-morbid diseases
- Patient smoking history [never a smoker, former smoker (previously smoked ≥ 10 pack year and has not smoked for at least 6 months prior to Visit 1), current smoker (10 pack year and smoked within 6 months prior to Visit 1); the number of pack years for former smoker and current smoker should be calculated (round up to the nearest integer)]
- Patient concomitant medication
- Pregnancy status
- Oxygen saturation
- Patient vital signs and Electrocardiogram (ECG)
- CAT score
- mMRC
- Pulmonary function test (spirometry): pre-dose FEV1, FVC, FEF₂₅₋₇₅ and IC
- Trelegy related AEs
- AEs that lead to the discontinuation of Trelegy
- SAEs

To be completed at Visit 2:

- Patient concomitant medication
- Pregnancy status
- Number of doses of Trelegy taken
- CAT score
- Trelegy related AEs
- AEs that lead to the discontinuation of Trelegy
- SAEs

To be completed at Visit 3 or E.D.:

- Patient concomitant medication
- Pregnancy status
- Number of doses of Trelegy taken
- Patient vital signs
- CAT score
- mMRC
- Pulmonary function test (spirometry): Pre-dosed FEV₁, FVC, FEF₂₅₋₇₅ and IC
- Trelegy related AEs
- AEs that lead to the discontinuation of Trelegy
- SAEs

Table 1 Visit flow chart and data collection schedule

Procedure	Conse nting	Treatment and Observation Period (Days)			E.D.	Notes E.D. = early discontinuation / withdrawal (within 7 days of study discontinuation)
Study visit	V0 ¹ Pre- Scree ning	V1 Screen, enroll & baseline (Day 1)	V2 (Day 28)	V3 End of Study (Day 84)		
Time Window Allowed (days)			±7	±10		
Informed consent ²	X					
Inclusion / exclusion criteria		X				
Demography		X				
Full physical examination including height and weight		X				
Smoking History		X				

Procedure	Conse nting	Treatment and Observation Period (Days)				Notes E.D. = early discontinuation / withdrawal (within 7 days of study discontinuation)
Medical history: past and current medical conditions		X				
Vital signs		X		X	X	
Oxygen saturation		X				
ECG		X				
Trelegy Taken worksheet			X	X	X	Number of doses of Trelegy taken should be documented weekly by the patients, and the investigators will review and record in EDC
CAT score ²		X	X	X	X	
mMRC ³		X		X	X	
Spirometry ⁴		X		X	X	

Procedure	Conse nting	Treatment and Observation Period (Days)				Notes E.D. = early discontinuation / withdrawal (within 7 days of study discontinuation)
Review of Study treatment related AEs		X	X	X	X	
Clinical judgment should be used to determine whether there is a relationship between study treatment and each occurrence of each AE/SAE.
 
Study treatment related adverse events must be recorded from V1.
 
Where a causality relationship is determined, this must be recorded as a study treatment related AE.
 
AEs not related to either study treatment or discontinuation from study treatment are not recorded, unless classified as SAE.

Review of AEs that lead to the discontinuation of Trelegy		X	X	X	X	
All AEs that lead to discontinuation from study treatment, whether judged related to study treatment or not, should be recorded.
 
All AEs that lead to withdrawal from the study whilst the participant is on study treatment, whether judged related to study treatment or not, should be recorded.

Procedure	Conse nting	Treatment and Observation Period (Days)				Notes E.D. = early discontinuation / withdrawal (within 7 days of study discontinuation)
SAEs review		X	X	X	X	All SAEs are recorded from the start of using Trelegy. Clinical judgment should be used to determine the relationship between study treatment and each occurrence of each AE/SAE. Where a causality relationship is determined, this must be recorded as a study treatment related SAE.
Pregnancy status		X	X	X	X	
Concomitant medication review		X	X	X	X	

1. V0 and V1 could occur on the same day, and V1 should be completed ≤ 7 days after V0.
2. If a participant is unable to attend to the clinic for Visit 2 under certain situation (e.g. COVID-19 impact or lockdown), it's acceptable to carry out the CAT assessment by telephone or other remote approaches.
3. mMRC: assessed by both patients and physicians will be collected, refers to 3.6.1.2.
4. Pre-dose FEV₁, FVC, FEF₂₅₋₇₅ and IC will be entered into eCRF.

3.2.1. Withdrawal from Trelegy or the Study

Participants that permanently stop Trelegy are not required to withdraw from the study. If for any reason a participant must permanently stop Trelegy, every effort should be made by the Investigator/delegate to keep the participant in the study to collect all the effectiveness and safety data of the subsequent visits per the Schedule of Activities (SoA) after the Trelegy discontinuation.

Any female participant who becomes pregnant while participating will be withdrawn from the study.

A participant may withdraw from the study at any time at his/her own request, or may be withdrawn at any time at the discretion of the investigator for safety, behavioural, or administrative reasons. If a participant withdraws from the study, he/she has to complete the E.D. visit per SoA ([Table 1](#)), and no more extra data will be collected after E.D. visit.

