4.2.2. Main analytical approach

Primary analysis will be conducted using an inverse-probability weighted mixed model for repeated measures (MMRM) for the change from baseline in CAT score under the missing at random (MAR) assumption to handle missingness which may occur during the data collection.

The inverse probability weighting (IPW) method can reduce the selection bias caused by the missingness, by weighting the participants whose change from baseline of CAT score is observed at week 12 using the inverse probability of completeness in the endpoint. The key assumption for the IPW method is MAR which means that the missingness mechanism of the primary endpoint could be modelled using the observed factors, i.e. the baseline covariates and the post-baseline covariates by the time of missingness, and no unmeasured confounders are involved in the missingness mechanism.

To estimate the probability of the completeness of the primary endpoint, a logistic model is constructed to model its missingness mechanism with the missingness status as the dependent variable (status=observed, status=missing as the reference group). The following baseline and post-baseline covariates will be considered for the missingness of change from baseline in CAT score at week 12:

- Age,
- Gender,
- Years of COPD,
- Smoking history: smoking status and number of pack years,
- Pre-dose FEV1 at baseline,
- COPD maintenance treatment at baseline,
- CAT score at baseline,
- The change from baseline in CAT score at week 4,
- Intercurrent event status: no intercurrent events, received other COPD maintenance therapy, Trelegy discontinued due to other reason.
The subjects receiving other COPD maintenance therapy are those who have discontinued their Trelegy therapy and switched to other COPD maintenance therapy.
- Duration of Trelegy

The right tail of estimated weights may be truncated by its appropriate percentile if deemed necessary.

The change from baseline in CAT score will be analysed using the MMRM model with the covariates of smoking status, CAT score at baseline, visit, the interaction of CAT score at baseline*visit, in which each observation is weighted with the inverse probabilities derived from the above logistic regression models.

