4.2.3. Sensitivity analyses

Sensitivity analysis will be conducted using a MMRM with the covariates of smoking status, CAT score at baseline, visit, the interaction of CAT score at baseline*visit to derive the point estimate and the standard error of change from the baseline in the CAT score, but in which the

missing data in the primary endpoint will be imputed using monotone linear regression multiple imputation under missing at random assumption, for participants with no intercurrent events, receiving other COPD maintenance therapy, with treatment discontinuation, separately if data permits, otherwise may be imputed for the pooled groups, using the observed factors, i.e. the baseline covariates and the post-baseline covariates by the time of missingness.

The missing values in the covariate may be imputed with information by time of its missingness if deemed necessary.

At least 1000 datasets will be generated which include both observed and imputed values for the covariates. The MMRM estimates for the primary endpoint as well as the corresponding standard errors from each complete dataset will be combined using the Rubin's rule.

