6.3.2. E.D. Data

To make full use of effectiveness outcomes data, the effectiveness measurements collected at E.D. including CAT score, mMRC and Pulmonary function test (Pre-dosed FEV₁, FVC, FEF₂₅₋₇₅ and IC) will be used according to the following rules:

- If E.D. date of the participant is before Day 55 ($<=55$), the participant's value of week 12 related endpoints will be treated as missing and its analysis approach can be found in Section 4. Otherwise, the participant's value of week 12 related endpoints will be mapped to E.D. results.
- If E.D. date of the participant is before Day 12 ($<=12$), the participant's value of week 4 related endpoints will be treated as missing and its analysis approach can be found in Section 4. Otherwise, the participant's value of week 4 related endpoints will be mapped to E.D. results, if E.D. date of the participant is before Day 21 ($<=20$).

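### A mandatory early-discontinuation CAT score from Days 21 to 55 is mapped to no visit and enters no planned estimate, so the MAR sensitivity analysis shares the primary analysis's blind spot

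*Protocol*

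**What the plan says.** Protocol 3.2.1 makes the E.D. visit compulsory on withdrawal from the study ("If a participant withdraws from the study, he/she has to complete the E.D. visit per SoA") and collects nothing after it. Table 1 lists CAT, mMRC and spirometry at that visit. Participants who only stop Trelegy stay in the study and are measured at Week 12.

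The operative rule is in SAP 6.3.2, which says it aims to use the effectiveness data fully:

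- **Week 12, early E.D.:** "If E.D. date of the participant is before Day 55" (the bracket beside it says Day 55 or earlier), the "value of week 12 related endpoints will be treated as missing and its analysis approach can be found in Section 4".
- **Week 12, later E.D.:** otherwise the "value of week 12 related endpoints will be mapped to E.D. results".
- **Week 4:** an E.D. date up to Day 12 leaves Week 4 missing. After that, the "value of week 4 related endpoints will be mapped to E.D. results, if E.D. date of the participant is before Day 21".

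SAP 4.2.2 weights observed values by the inverse probability of being observed. The only post-baseline score in the Week 12 missingness model is "The change from baseline in CAT score at week 4"; intercurrent event status and duration of Trelegy are also listed. SAP 4.2.3 imputes missing values by monotone regression under MAR, "using the observed factors, i.e. the baseline covariates and the post-baseline covariates by the time of missingness". It neither names nor excludes the E.D. CAT.

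**The concern.** A participant who withdraws on Day 45 has a CAT on file that is newer than Week 4 and was taken at the moment of leaving. The plan makes that score compulsory and then gives it no place.

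The study has no control arm and is meant to support licence renewal. If withdrawal follows worsening after Week 4, the mean fall in CAT is overstated. The sensitivity analysis relies on MAR with the same post-baseline CAT information as the primary analysis, so agreement between the two would not reveal the problem.

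**Working it through.** **1. Where an E.D. CAT goes, by study day (SAP 6.3.2)**

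| E.D. day | Week 4 | Week 12 |
|---|---|---|
| 1-12 | missing | missing |
| 13-20 | E.D. value used | missing |
| 21-55 | no mapping | missing |
| 56 onward | no mapping | E.D. value used |

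Up to Day 55 the E.D. CAT is used nowhere on 12 + 35 = 47 of 55 days. Days 21-35 lie inside the Visit 2 window (Day 28 ± 7, Protocol Table 1). Even there, if Visit 2 was not done, the E.D. CAT does not become the Week 4 value.

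**2. Can the wording of SAP 4.2.3 admit it?** Not as an ordinary predictor. A monotone regression takes its slopes from participants with Week 12 observed, and none of them has an E.D. CAT from Days 21-55. The logistic model fails for the same reason: the value exists only when Week 12 is missing. It can enter only as an observation at a known study day.

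**3. The plan's own precision figure.** Inputs from Protocol 3.7 are N = 460, group shares 79/20/1%, means -2/-2/0 and SD 7. The mixture mean is -1.98 and the SD 7.003, as in Table 2. Half-width = 1.96 × 7.003 / √n_eff, where n_eff = N / Σ[p/(1 - m)], p is the group share and m its missing proportion.

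- Scenario 1: n_eff = 460, half-width 0.640 (stated 0.64).
- Scenario 2: Σ = 0.79/0.95 + 0.20/0.70 + 0.01/0.50 = 1.137, n_eff = 404.5, half-width 0.682 (stated 0.69).
- Scenario 3: Σ = 0.79/0.90 + 0.20/0.50 + 0.01/0.30 = 1.311, n_eff = 350.8, half-width 0.733 (stated 0.73).

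The plan's figures reproduce closely. The missing shares are:

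- Scenario 2: 0.79×0.05 + 0.20×0.30 + 0.01×0.50 = 10.45%, or 48 of 460.
- Scenario 3: 0.79×0.10 + 0.20×0.50 + 0.01×0.70 = 18.6%, or 86 of 460.

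**4. Size of the bias.** The documents give no E.D. timing, within-person correlation or link between worsening and withdrawal, so these are assumptions. CAT change was simulated in 400,000 participants at Days 28, 45 and 84:

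- SD 7 and a flat mean over time.
- Day 28 to Day 84 correlation of 0.4, 0.55 or 0.7, either decaying exponentially with time or constant.
- Withdrawal at Day 45 in 3, 6 or 9%, with log-odds rising by 0.08 or 0.15 per CAT unit on that day.

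The time-scaled slope from Day 45 is r^((84-45)/(84-28)) = r^(39/56), that is 0.53 for r = 0.4 and 0.78 for r = 0.7. Bias is estimate minus truth; negative favours Trelegy.

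| Week 12 obtained from | Exponential decay true | Constant correlation true |
|---|---|---|
| Week 4 CAT only | -0.02 to -0.14 | -0.02 to -0.15 |
| E.D. CAT, time-scaled slope | -0.01 to 0.00 | +0.01 to +0.07 |

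Under exponential decay, weighting on Week 4 instead of imputing gave nearly the same figures as the first row. Using the raw Day 45 value as Week 12 errs the other way, by +0.02 to +0.33 across both structures.

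Against the planned half-widths, the worst case is 0.15/0.73 = 21% to 0.15/0.69 = 22%. Against the assumed 2-unit effect it is 0.15/2 = 7.5%.

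**5. Spirometry and mMRC.** Neither has a Week 4 assessment, so E.D. values up to Day 55 enter no endpoint analysis. This affects two secondary endpoints (mMRC, FEV1) and three exploratory ones (FVC, FEF25-75, IC). No bias was calculated for these.

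**The case against.** The strongest defence is that leaving Week 12 missing after an early E.D. visit is a sound choice. The estimand is the Week 12 change under treatment policy, and reading a Day 30 or Day 45 score as Week 12 is last value carried forward. That stands: the cut-off is not the fault. What is missing is a route for the score to inform the imputation.

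It is also fair that the weights include intercurrent event status and duration of Trelegy, which carry some withdrawal information that the simulation omits. They do not record whether the participant had improved or worsened.

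The assumptions are demanding at the upper end. Nine per cent of 460 is about 41 people, or 86% of all Scenario 2 missingness, all leaving near Day 45 with an E.D. CAT. Some of the missing will be unreachable and have no E.D. visit, and some will withdraw for administrative reasons or pregnancy. No hypothesis is tested.

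Finally, the near-zero residual under exponential decay is partly circular, because the correction uses the form that generated the data. The constant-correlation column is the fairer test: the error shrinks but changes sign.

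**Conclusion.** The gap is real and specific. An E.D. CAT on Days 21-55 reaches no planned estimate, and the SAP's general wording cannot bring it in. The resulting bias favours Trelegy by about 0.02-0.15 units if withdrawal tracks worsening after Week 4. It would be small if withdrawal does not. The change is worth making, but the bias does not threaten the study's main conclusion.

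A reader might infer more, and the documents do not support it:

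- **That all E.D. data up to Day 55 are ignored.** For CAT, Days 13-20 serve as Week 4 and so reach both the MMRM and the missingness model.
- **That the primary analysis imputes withdrawers from old data.** It up-weights observed participants.
- **That Protocol 3.2.1 is at fault.** It only requires the visit.
- **That the bias could match the confidence interval's half-width.** If all 18.6% missing in Scenario 3 had an unused E.D. CAT and were 4 points worse than modelled, the shift would be 0.186 × 4 = 0.74. Nothing in the documents suggests either condition.

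**What to change.** 1. In SAP 6.3.2, map an E.D. CAT on Days 21-35 to Week 4 when no Visit 2 CAT exists. In the same edit, reconcile the one-day mismatches between the wording and the brackets at Day 55 and Day 12.
2. In SAP 4.2.3, add an analysis that enters the E.D. CAT from Days 21-55 at its actual study day, together with Visit 2 and Visit 3, in an imputation model whose correlation decays with time. Each score enters once. Impute Week 12 from that model and show the result beside the planned MAR result.
3. For spirometry and mMRC, any analysis that takes an E.D. value up to Day 55 as Week 12 should be optional and labelled as last value carried forward.

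The cost is SAP wording and a few lines of code; the data are already collected. There are three limits:

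- The decay form must be assumed, because completers inform the correlation mainly at the nominal gap of 84 - 28 = 56 days. The residual error was about -0.01 to +0.07 in the cases tried.
- Participants lost without an E.D. visit are not helped.
- The primary IPW-MMRM method is unchanged. Only item 1 reaches it, by supplying some Week 4 values.
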